**Coronary ARteriogenesis with combined Heparin and
EXercise therapy in chronic refractory Angina (CARHEXA):
A phase 3 double-blind, placebo-controlled, parallel group
study**

December 25, 2012

ABSTRACT

Background: Although experimental studies on the stimulation of coronary arteriogenesis have been promising, not a single drug has been proved to be applicable in clinical practice, either due to lack of efficacy or because of undesired side effects. Encouraging results have been obtained with combination of heparin (H) coupled with a stress inducing ischemia and augmenting shear stress, such as exercise.

Aim: to establish the coronary arteriogenetic efficacy of H combined with exercise in patients with intractable coronary artery disease.

Methods: We will recruit 60 "no-option" patients with chronic stable angina refractory to optimal medical management, and not suitable for percutaneous and/or surgical revascularization therapy. As further inclusion criteria eligible patients are able to exercise (and enter a cardiac rehabilitation program). In a prospective, randomized, double-blind study design these "no-option" patients will be allocated (30 for each of the 2 groups) to one of 2 treatment groups: 1) standard physical rehabilitation (i.v. placebo 10 min prior to each of 2 exercise session per day for 5 days a week for 2 weeks); 2) drug-primed physical rehabilitation (same modality as 1, but with H, 100 UI/Kg up to a maximum of 5.000 IU iv, 10 min prior to the exercise). All patients will undergo exercise stress echo (with wall motion score index, coronary flow reserve on left anterior descending and global longitudinal strain evaluation) and cardiac CT (with coronary collateral assessment) both before and after the therapy cycle.

Endpoints. Clinical and imaging (by blinded observers) assessment will be performed before and after treatment. **Primary clinical endpoint** is Canadian Cardiovascular Society (CCS) angina severity, ranging from class 1 (mild) to 4 (severe). **Secondary stress imaging functional endpoint** is peak Wall Motion Score Index (WMSI) at stress echo (ancillary endpoints: global longitudinal strain and coronary flow reserve). **Tertiary imaging endpoint** is Coronary Collateral Circulation Score at cardiac CT.

Epidemiological and clinical background

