Our approach is based on the combination of pharmacological stimuli (with heparin) on top of a 2-week cycle of physical rehabilitation (in patients capable to exercise). The rationale for this chemical-physical cocktail stems from the fact that increase in shear stress (achieved with exercise), or heparin – when used alone - have no significant coronary arteriogenic effect, which is consistently present, and clinically significant, when the two stimuli are coupled (*Fujita M et al. 1988*). The basic principle of heparin treatment is potentiation of angiogenic growth factors, which

are overexpressed by increased shear stress at the site of pre-existing collateral vessels as a result of exercise or pacing. Although the precise mechanisms by which heparin potentiates arteriogenesis remain to be completely elucidated, heparin administration combined with exercise (*Tateno S et al 2001*) has great potential in treating patients with effort angina who are not indicated for conventional reperfusion therapy.

Study hypothesis

In the large and expanding population of "no-option" patients with refractory angina, a clinically significant coronary arteriogenic effect can be obtained through a combination of pharmacological (heparin) and physical (rehabilitation exercise program) stimuli, when used in combination.

Overall study design

We will recruit 60 patients with chronic stable angina refractory to medical management, and not suitable for percutaneous and/or surgical revascularization therapy. As additional criterion for treatment eligibility, patients will have exercise capacity allowing to enter a rehabilitation program. In a prospective, randomized, open-label study design these "no-option" patients will be allocated (30 for each group) to 2 treatments: 1) standard physical rehabilitation (2 exercise session per day for 5 days a week for 2 weeks); 2) drug-primed physical rehabilitation (same modality as 1, but with H, 100 UI/Kg up to a maximum of 5.000 IU iv, 10 min prior to the exercise). All patients will undergo exercise stress echo (with wall motion score index, coronary flow reserve on left anterior descending and global longitudinal strain evaluation) and cardiac CT (with coronary collateral assessment) both before and after then therapy cycle.

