Inclusion criteria: patients with documented coronary artery disease not amenable of further treatment and belonging to the "no-option" category (see above definition), with symptoms consistent with angina pectoris.

Exclusion criteria: patients with unstable angina, recent acute myocardial infarction, uncontrolled hypertension, haemodynamically significant valvular heart disease, bronchial asthma and neurologic and/or orthopedic illnesses that limit exercise capacity will be excluded. Patients receiving vitamin K antagonist will be excluded. Patients should not be actively involved in programmes of cardiac rehabilitation or exercise training.

All medications will remain unaltered during the study

Clinical and imaging (by blinded observers) assessment will be performed before and after treatment. **Primary clinical endpoint** is Canadian Cardiovascular Society (CCS) angina severity, ranging from class 1 (mild) to 4 (severe). **Secondary stress imaging functional endpoint** is peak Wall Motion Score Index (WMSI) at stress echo (ancillary endpoints: global longitudinal strain and coronary flow reserve). **Tertiary imaging endpoint** is Coronary Collateral Circulation Score at cardiac CT.

Detailed Work Plan

The overall architecture of the project is structured into work-packages (WP) that will be run by separate teams, in parallel with each other:

WP0- Study design and statistical plan

WP1- Patient recruitment and treatment

WP2-Assessment of treatment effect on inducible ischemia by stress echo

WP3- Assessment of Coronary Collateral Circulation by MDCT

WP0- Study design and Statistical plan

Sample size calculation. The study is sized to detect with 80% power a clinically significant difference in the chosen endpoints with $\alpha=0.05$. For primary endpoint, a Canadian Class Angina = 2.5, with 0.5 standard deviation, and with an expected, clinically significant improvement of 0.5 will lead to a sample size of 16 patients per arm (94 % power with 25 patients per arm). For secondary endpoint, a peak WMSI = 1.4, with 0.25 standard deviation, and with an expected, clinically significant improvement of 0.2 will lead to a sample size of 25 patients per arm. Overall a drop-out rate of 20 % is expected, and therefore 60 patients will be initially considered and 50 are expected to complete the trial (25 for each arm)

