Statistical plan: All continuous data will be given as mean+ SD. Baseline characteristics between the groups will be analyzed by Student t test for continuous data and chi-square/Fisher exact test for categorical data. Outcomes at follow-up examinations will be analyzed with chi-square test (for angina class) and paired Student t test (for approximately normally distributed data such as Wall Motion score index). Differences are considered statistically significant at a 2-sided P value of

<0.05. Electronic Case Report form preparation, ad interim and final data analysis will be performed by the Biometry Unit of the Institute of Clinical Physiology.

Core lab reading: All imaging data will be read by a single reader blinded to patient identity and study conditions.

Expected results: The group treated with active drug therapy will show a significant improvement of clinical, functional and perfusion indices when compared to standard rehabilitation therapy

WP1- Patient recruitment and treatment

CARHEXA is a prospective, randomized, single-center study: clinical enrollment and data collection will be done by Belgrade Unit. The Belgrade center has a recent tradition of clinical and scientific excellence in the field of diagnosis and treatment of coronary artery disease and has the facilities required to complete the study.

Ethical Committee submission will be presented at local authority by the Belgrade Unit, also responsible of clinical enrollment and data collection. We will recruit 60 patients with chronic stable angina refractory to medical management and not suitable for percutaneous and/or surgical revascularization therapy (see the above definition of “no-option” patients). In a prospective, randomized, open-label study design these "no-option" patients will be allocated (30 for each of the 2 groups) to one of 2 treatment groups: 1) standard physical rehabilitation (2 exercise session per day for 5 days a week for 2 weeks) with placebo (iv saline 10 min prior to exercise) ; 2) drug-primed physical rehabilitation (same modality as 1, but with H, 100 UI/Kg up to a maximum of 5.000 IU iv, 10 min prior to the exercise).

The Canadian Cardiovascular Society (CCS) classification of angina severity, ranging from class 1 (mild) to class 4 (severe), is used routinely in patients with coronary artery disease and is a recognized marker for disease progression.

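### A 20% drop-out from 60 patients leaves 48 completers (24 per arm), not the stated 50 (25 per arm), and on the plan's own inputs WMSI power is then 79%, just under the stated 80%

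*Combined protocol and SAP*

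**What the plan says.** All the sizing is in one paragraph, WP0, Sample size calculation. It opens with a general claim: "The study is sized to detect with 80% power a clinically significant difference in the chosen endpoints", at alpha 0.05.

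- **Primary endpoint, CCS class:** mean 2.5, SD 0.5, improvement 0.5. The plan says this "will lead to a sample size of 16 patients per arm (94 % power with 25 patients per arm").
- **Secondary endpoint, peak WMSI:** "a peak WMSI = 1.4, with 0.25 standard deviation", and an expected "clinically significant improvement of 0.2 will lead to a sample size of 25 patients per arm".
- **Drop-out:** "a drop-out rate of 20 % is expected, and therefore 60 patients will be initially considered and 50 are expected to complete" the trial, given as 25 for each arm.

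The 60 is the number randomised. The Abstract (Methods) and WP1 both say "patients will be allocated (30 for each of the 2 groups) to one of 2 treatment groups", and Overall study design says "patients will be allocated (30 for each group) to 2 treatments". No other drop-out rate or completer count appears anywhere. The Statistical plan in WP0 sets two-sided testing at 0.05.

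**The concern.** The drop-out rate, the intake and the number of completers cannot all be true. The sentence presents 60 as following from the 20%, but 60 less 20% is 48. Taking the 60 as a screening number would remove the conflict, but three other sections allocate all 60 to treatment.

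WMSI is the endpoint at stake. CCS class needs only 16 per arm, so WMSI fixes the trial at 25 per arm. If the stated drop-out leaves fewer than 25, the 80% power claimed for the chosen endpoints may fail for the endpoint that determined the trial's size. The 94% quoted for CCS is also tied to 25 per arm, a number that the stated drop-out does not leave.

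**Working it through.** **Inputs.** From WP0, Sample size calculation: alpha 0.05, target power 80%, WMSI difference 0.2 with SD 0.25, CCS difference 0.5 with SD 0.5, drop-out 20%, 60 enrolled. From WP0, Statistical plan: two-sided testing. From the Abstract, Overall study design and WP1: equal allocation, 30 per arm. The standardised difference d is 0.2/0.25 = 0.8 for WMSI and 0.5/0.5 = 1.0 for CCS.

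**Step 1. Reproduce the plan's figures.** The normal approximation for two independent means gives n per arm = 2 × (1.960 + 0.842)² / d², and power = Φ(d × √(n/2) − 1.960).

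- WMSI: n = 24.53, rounded up to 25. Matches.
- CCS: n = 15.70, rounded up to 16. Matches.
- CCS power at 25 per arm: Φ(1.0 × √12.5 − 1.960) = 94.2%. Matches the 94%.

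All three figures reproduce by this one method.

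**Step 2. Drop-out.**

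- 60 × (1 − 0.20) = 48, so 24 per arm.
- 1 − 50/60 = 16.7%, the loss that would leave 50.
- 50 × 1.2 = 60. Adding 20% of the completers gives exactly the plan's number.
- 50 / (1 − 0.20) = 62.5, the intake that 50 completers require. With equal arms this is 64.

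**Step 3. Power at the completers that 20% drop-out leaves.**

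| Endpoint | Per arm | Normal approximation | Noncentral t |
|---|---|---|---|
| WMSI (0.2, SD 0.25) | 25 | 80.7% | 79.1% |
| WMSI | 24 | 79.1% | 77.4% |
| CCS (0.5, SD 0.5) | 25 | 94.2% | 93.4% |
| CCS | 24 | 93.4% | 92.4% |

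For WMSI at 24 per arm, Φ(0.8 × √12 − 1.960) = Φ(0.811) = 79.1%. The requirement was 24.53 per arm, so 24 falls just short. Put another way, 80% power at 24 per arm needs a WMSI difference of 0.202 (normal) or 0.207 (t) instead of 0.20.

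**Step 4. How much is due to drop-out.** Going from 25 to 24 per arm costs about 1.6 to 1.7 points of WMSI power by either method. By the noncentral t, WMSI needs 25.52 per arm, so 26 (80.7%). On that stricter method 25 per arm is already slightly short before any question of drop-out.

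**The case against.** The strongest reply is that almost nothing follows from this. The gap is one patient per arm and about one power point against the 80% target. An SD of 0.247 instead of 0.25 would restore 80% at 24 per arm, and the plan gives the SD to two decimals with no source, so the shortfall lies within rounding of an assumption. This is fair. It settles the severity, but it does not make 48 equal 50.

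A second reply is that the noncentral t should not be held against the plan. The plan names no power method, and its figures reproduce by the normal approximation. This also stands, and the standard would have to be applied evenly: by the noncentral t the 16 per arm for CCS gives only 78.1%. The t figures are therefore a sensitivity check. The finding does not need them, because the 80% line is crossed under the plan's own method.

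A third reply is that these powers are conditional. They are for a two-sample comparison of means, whereas the Statistical plan says: "Outcomes at follow-up examinations will be analyzed with chi-square test (for angina class) and paired Student t test". The documents give neither an SD of change nor a correlation, so the power of a paired test cannot be worked out from them. That is correct. The 79% tests the sizing calculation and does not describe the power of the named analyses. Whether those analyses suit the question is a separate matter.

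**Conclusion.** The point holds and is minor. At the stated 20% drop-out, 60 patients yield 48 completers (24 per arm), not 50 (25 per arm). This is simple arithmetic and rests on no statistical assumption.

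On the plan's own inputs, the loss takes WMSI power from 80.7% to 79.1% by the normal approximation (79.1% to 77.4% by the noncentral t), so the 80% claim does not hold for the secondary endpoint. The primary endpoint keeps power above 90%. The sizes of 16 and 25 per arm are correct by the method that reproduces them; the error lies in the drop-out step. The power figures assume a two-sided two-sample comparison of means at alpha 0.05, equal arms, and the stated SDs and differences.

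**What to change.** Rewrite the drop-out and power statements in WP0, Sample size calculation, along these lines:

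> Sixty patients will be enrolled (30 per arm). With 20% drop-out, 48 are expected to complete (24 per arm). For a two-sided two-sample comparison of means at alpha 0.05, power by normal approximation (noncentral t) is 79% (77%) for WMSI (difference 0.2, SD 0.25) and 93% (92%) for CCS class (difference 0.5, SD 0.5). These figures do not describe the power of the chi-square and paired t tests named in the statistical plan.

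Amend the opening sentence of the paragraph so that it no longer claims 80% power for WMSI. The cost is one paragraph with slightly less favourable figures. It needs no extra patients and no change to the analysis.

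Only if the sponsor prefers to keep the 80% claim for WMSI does the intake need to rise:

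- **Normal approximation:** 25 completers per arm (80.7%) takes 50/0.8 = 62.5, so 64 enrolled (32 per arm), 4 more than planned.
- **Noncentral t:** 26 completers per arm (80.7%) takes 52/0.8 = 65, so 66 enrolled (33 per arm), 6 more than planned.

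### The primary endpoint's stated sample size and power belong to a two-sample comparison of mean CCS class and are not supported for the chi-square test that the plan names

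*Combined protocol and SAP*

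**What the plan says.** The endpoints paragraph before the Detailed Work Plan defines the primary endpoint as "Canadian Cardiovascular Society (CCS) angina severity, ranging from class 1 (mild) to 4 (severe". This is an ordered four-class scale. The same paragraph says "Clinical and imaging (by blinded observers) assessment will be performed before and after treatment", so a baseline class is collected.

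WP0, Sample size calculation, sets the aim: "The study is sized to detect with 80% power a clinically significant difference in the chosen endpoints". For the primary endpoint it assumes "a Canadian Class Angina = 2.5, with 0.5 standard deviation, and with an expected, clinically significant improvement of 0.5", and says that this "will lead to a sample size of 16 patients per arm (94 % power with 25 patients per arm". The size actually planned, 25 completers per arm, comes from the wall motion endpoint: "improvement of 0.2 will lead to a sample size of 25 patients per arm".

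WP0, Statistical plan, gives the analysis: "Outcomes at follow-up examinations will be analyzed with chi-square test (for angina class", followed by "paired Student t test (for approximately normally distributed data such as Wall Motion score index". The significance level is two-sided 0.05. Nothing says whether the chi-square uses class order, how the table is laid out, or whether baseline class enters. Fisher's exact test is mentioned only for baseline comparisons. No class proportions are given for either arm.

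**The concern.** The only power statement for the primary endpoint uses a mean, an SD and a difference in means. The named test compares frequencies. An ordinary chi-square ignores the order of the classes, so it spreads its sensitivity over every possible difference in shape. For a steady shift towards milder classes, it usually has less power than a test that uses the order.

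With about 50 completers, the trial cannot afford to lose power through the choice of test. The sponsor would also be quoting 94% for an analysis for which that figure was never calculated.

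**Working it through.** **Inputs.** From WP0: mean 2.5, SD 0.5, difference 0.5, two-sided 0.05, 16 and 25 per arm. The class distributions below are assumptions.

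**1. Reproduce the plan's figures.** For two means, n per arm = 2(z₀.₉₇₅ + z₀.₈₀)²(SD/difference)² = 2(1.960 + 0.842)²(0.5/0.5)² = 15.7, rounded up to 16. Power = Φ(√(n/2) × difference/SD − 1.960):
- n = 16: Φ(2.828 − 1.960) = 80.7%
- n = 25: Φ(3.536 − 1.960) = 94.2%

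A t test gives 78.1% and 93.4%. One-sided (13 per arm, 97.1%) and paired (10, 99.8%) calculations do not fit. The plan's figures are therefore those of a two-sided, two-sample comparison of means.

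**2. Turn the mean and SD into classes.** Every whole-number class lies at least 0.5 from 2.5, so the variance is at least 0.25. SD 0.5 is thus the smallest possible at mean 2.5, and it forces controls to 50% in class 2 and 50% in class 3.

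For the treated arm, assume the same SD at mean 2.0. Writing p for class shares, the mean gives p₁ = p₃ + 2p₄ and the variance gives p₁ + p₃ + 4p₄ = 0.25. Hence p₃ = 0.125 − 3p₄, with p₄ between 0 and 1/24 (4.2%). With p₄ = 0 the treated arm is 12.5/75/12.5% in classes 1/2/3.

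**3. Simulate power at p₄ = 0** (40,000 to 60,000 trials, uncorrected Pearson test on the occupied classes):

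| Between-arm test | 16 per arm | 25 per arm |
|---|---|---|
| Unordered chi-square | 60% | 86% |
| Rank test | 76% | 93% |
| Linear-trend chi-square | 78% | 94% |
| t test | 78% | 94% |

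The unordered test first passes 80% at about 23 per arm.

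**4. Vary the treated arm, with controls still 50/50.** Unordered chi-square:

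| Treated arm, mean 2.0 | 16 per arm | 25 per arm |
|---|---|---|
| SD 0.5, 1% in class 4 | 68% | 90% |
| SD 0.5, 2% in class 4 | 76% | 95% |
| SD 0.5, 4.2% in class 4 | 97% | over 99% |
| SD 0.40, none in class 4 | 73% | 93% |
| SD 0.32, none in class 4 | 84% | 97% |
| SD 0.25, none in class 4 | 91% | 99% |

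At a 4.2% class 4 share, the unordered test beats the t test (90%) and the rank test (98%) at 25 per arm. It is then reacting to treated patients in the worst class, which is not evidence of benefit.

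**5. Sensitivity outside the stated inputs.** With a share s of controls in each of classes 1 and 4, and the rest split equally between classes 2 and 3, the variance is 0.25 + 4s. One percent in each gives SD √0.29 = 0.54. Rounded normal scores, 25 per arm:

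| Class SD | Unordered chi-square | Rank test |
|---|---|---|
| 0.51 | 82% | 91% |
| 0.53 | 78% | 89% |
| 0.58 | 69% | 84% |
| 0.62 | 60% | 78% |

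At SD 0.58, an exact version of the unordered test has 73%. About 4 of the roughly 16 points lost are therefore sparse-cell conservatism, and about 12 come from ignoring order. Under the null at that SD, the unordered test rejects in 2.8% of trials and the rank test in 5.0%.

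**The case against.** The strongest reply is that the commitment is 80% power, the trial is planned with 25 completers per arm and not 16, and on the plan's own mean and SD the all-class chi-square keeps 80% there. That stands. Several stronger readings are tempting and are not supported:

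- **A reader might infer that the trial is underpowered.** Every all-class figure below 80% at 25 per arm needs an SD above the stated 0.5. It is then partly a challenge to the SD: at 0.62 the rank test also misses 80%. A table of classes 1–2 against 3–4 with Yates correction would give 75–76% even at the stated inputs. The plan names neither that grouping nor the correction, and uncorrected the same table gives 86%.
- **A reader might infer that 16 per arm is generally too few.** The plan gives no separate SD for the treated arm, and nothing weights one class 4 share against another. Step 4 includes cases above 80% at 16 per arm.
- **A reader might infer that the chi-square always loses power.** Step 4 shows the contrary.
- **A reader might infer that an improved/not improved table is planned and calculate its power.** That would need a correlation between baseline and follow-up class, which the documents do not give.

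It is also fair to say that chi-square test could mean a linear-trend version, which nearly matches the stated figures. Nothing in the text says so, and the usual meaning is the unordered test. Finally, the between-arm intent is reasonably clear from the randomised design and the Expected results paragraph. The paired t test for wall motion is a separate matter.

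**Conclusion.** The point holds as a mismatch that should be fixed. The 16 per arm and 94% are correct arithmetic for a comparison of means, but they are not supported for the chi-square that the plan names.

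With SD 0.5 in both arms and no treated patient in class 4, the unordered test gives up about 7 points against a rank test at 25 per arm (86% against 93%) and about 16 at 16 per arm (60% against 76%). The 80% target survives at 25 per arm on those inputs. These sizes rest on assumed class distributions, and some others remove or reverse the gap.

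The margin deserves attention because the stated SD is the smallest that the scale allows at that mean. A modest increase to about 0.53 takes the unordered test to 78% under rounded normal scores, while a rank test stays at 89%. No false-positive inflation is claimed; the simulated unordered test is conservative.

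**What to change.** In WP0, Statistical plan, replace the chi-square as the primary test with one prespecified, two-sided, between-arm test of follow-up CCS class that uses class order and, preferably, baseline class. One example is a rank or trend test stratified by baseline class 1–2 against 3–4. Pooling the baseline classes is sensible: in simulation with four strata at SD 0.58, 74% of trials had an extreme baseline class filled from one arm only. Keep the table of classes as descriptive and state its layout.

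In WP0, Sample size calculation, restate power at 25 per arm for the chosen test under a stated class distribution for each arm.

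The cost is wording and one new power calculation, with no new patients or data. There are two downsides. The restated power may fall below 94%. Stratification costs about 1 point if baseline class turns out to be uninformative; its gain otherwise depends on a baseline-to-follow-up correlation that the documents do not give. A plain trend test would close the gap with the sizing at least effort, but it would leave the collected baseline class unused.

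### The only test named for follow-up peak WMSI is a paired t test, so the plan names no heparin-versus-placebo test for its secondary endpoint

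*Combined protocol and SAP*

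**What the plan says.** The Statistical plan paragraph of WP0 separates baseline from follow-up. For baseline: "Baseline characteristics between the groups will be analyzed by Student t test for continuous data". For follow-up: "Outcomes at follow-up examinations will be analyzed with chi-square test (for angina class"), and for continuous outcomes a "paired Student t test (for approximately normally distributed data such as Wall Motion score index"). No unpaired t test, ANCOVA, mixed model or treatment-by-time test is named for follow-up WMSI anywhere in the document.

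Peak WMSI is the secondary endpoint, with global longitudinal strain and coronary flow reserve as ancillary endpoints. The sentence gives WMSI only as an example of approximately normal data, so it is reasonable to read the paired test as covering those two as well.

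The intended comparison is in Expected results, also in WP0: "The group treated with active drug therapy will show a significant improvement of clinical, functional and perfusion indices when compared to standard rehabilitation therapy". The sample size paragraph gives, for WMSI with SD 0.25, that a "clinically significant improvement of 0.2 will lead to a sample size of 25 patients per arm". For the primary endpoint, CCS class, the corresponding figure is 16 per arm.

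**The concern.** A paired t test needs values that belong together in pairs. Patients are randomised to two independent arms and nothing in the document matches them across arms. The pairing must therefore lie within the patient, and before versus after treatment is the natural reading. That test asks whether WMSI changed, not whether it changed more on heparin.

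The distinction matters here because WP1 gives both arms the same rehabilitation; the active arm is "drug-primed physical rehabilitation (same modality as 1, but with H" added. Training, repeat stress testing and regression to the mean can move WMSI in both arms, and a before-after test credits all of that movement to whichever arm is tested. The section on pharmacologic approaches says that exercise or heparin used alone "have no significant coronary arteriogenic effect". That concerns arteriogenesis and does not rule out these other sources, whose size is unknown.

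WMSI also sets the size of the trial, because it needs 25 per arm against 16 for CCS class. The named analysis does not use the two-arm comparison that those patients are recruited for. The test for CCS class is outside this point.

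**Working it through.** **Inputs from the WP0 sample size and statistical paragraphs.** Difference 0.2, SD 0.25, 80% power, two-sided 0.05, 25 completers per arm.

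**Assumed, because the documents do not give them.** Before-after correlation r = 0.3, 0.5 or 0.7; a change shared by both arms of 0, 0.05 or 0.10 (0.20 as an extreme); and 0.25 read as the SD at one visit. With r = 0.5 the SD of change is also 0.25, so the r = 0.5 results for the paired test and for the test on change also apply if the plan meant 0.25 as the SD of change.

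**1. The plan's own figure.** Two independent means, normal approximation:

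n per arm = 2 × (1.960 + 0.842)² × 0.25² / 0.2² = 2 × 7.849 × 0.0625 / 0.04 = 24.5, rounded up to 25.

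This matches the plan. By noncentral t, 25 per arm gives 79.1% power and 26 gives 80.7%. The same two-sample formula for CCS class (difference 0.5, SD 0.5) gives 2 × 7.849 × 0.25 / 0.25 = 15.7, so 16, again as stated.

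**2. Would a paired formula give 25?** The SD of change is 0.25 × √(2(1 − r)), and n = 7.849 × (SD of change)² / 0.04.

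| r | (SD of change)² | n |
|---|---|---|
| 0 | 0.1250 | 24.5 |
| 0.3 | 0.0875 | 17.2 |
| 0.5 | 0.0625 | 12.3 |
| 0.7 | 0.0375 | 7.4 |

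A paired formula reaches 24.5 only if a patient's before and after values are uncorrelated. The sizing is naturally read as between-arm.

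**3. What the paired test does when heparin has no effect.** In a heparin arm of 25, the noncentrality is (shared change × √25) / SD of change, with 24 degrees of freedom. For example, at a shared change of 0.10 and r = 0.5 it is 0.10 × 5 / 0.25 = 2.0, and the test is significant with probability 0.484. If p is the probability of significance in one arm, a significant result on heparin but not on placebo has probability p(1 − p); in the example, 0.484 × 0.516 = 0.250.

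| Shared change | Heparin arm significant (r = 0.3 / 0.5 / 0.7) | Heparin significant, placebo not |
|---|---|---|
| 0 | 5% / 5% / 5% | 5% / 5% / 5% |
| 0.05 | 13% / 16% / 24% | 11% / 13% / 18% |
| 0.10 | 37% / 48% / 70% | 23% / 25% / 21% |
| 0.20 | 90% / 97% / 99.9% | 9% / 3% / 0.1% |

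The last column rises and then falls, because a large shared change makes both arms significant. In the zero row the tests are two-sided, so only about half of the 5% (2.4%) is apparent benefit. In simulation (20,000 trials per cell, shared change 0, 0.05 and 0.10), the type I error of a between-arm ANCOVA was 4.8% to 5.2%.

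**4. Power of the between-arm alternatives for a true difference of 0.2** (noncentral t; ANCOVA residual SD = 0.25 × √(1 − r²)).

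| Test | 25 per arm (r = 0.3 / 0.5 / 0.7) | 24 per arm, r = 0.3 |
|---|---|---|
| ANCOVA, baseline as covariate | 83% / 89% / 97% | 81% |
| Unpaired t on change | 65% / 79% / 95% | 63% |
| Unpaired t on follow-up value | 79% / 79% / 79% | 77% |

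The 24-per-arm column is included because 20% dropout from 60 leaves 60 × 0.8 = 48 patients, not the 50 stated.

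**The case against.** The strongest reply is that this is a slip of wording. The sample size is two-sample, Expected results states a comparison with standard rehabilitation, and the chi-square test in the same sentence is ordinarily a test of independent groups. The word may have been meant as unpaired, or a between-arm test of each patient's change may have been left unsaid. That is plausible and the documents cannot settle it. The aim is not in doubt, but the named test does not serve it. An analyst who departs from the text would have to choose a replacement after the fact, and at r = 0.3 the candidates differ in power from 65% to 83%.

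Second, the plan contains no rule that heparin will be declared effective from within-arm P values, so the rates in step 3 are not error rates of this trial. That is correct. They show what the named test would respond to, under correlations and shared changes that are assumed.

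Third, WMSI is a secondary endpoint. True, but it is the one that determines the sample size.

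Fourth, WP2 has WMSI measured at rest and at peak stress, so the pairing could be rest versus peak. That would not compare the arms either.

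**Conclusion.** The concern holds. As written, the plan applies a within-patient test to peak WMSI and names no test of heparin against placebo for it. This follows from the text and the parallel-group design and needs no assumption. It must be corrected, because following the plan literally answers a different question from the one the trial randomises patients to answer.

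The possible consequence depends on a shared change that the documents do not give. With none, the heparin-arm paired test keeps its 5% level. With a shared improvement of 0.10, half of the plan's clinically significant 0.2, it is significant in 37% to 70% of trials with no heparin effect, for correlations of 0.3 to 0.7. The extension to strain and flow reserve is an inference from the plan's wording.

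**What to change.** Replace the paired t test in the WP0 statistical plan with a between-arm analysis, for example: *Follow-up peak WMSI will be compared between arms by ANCOVA with treatment arm as factor and baseline peak WMSI as covariate; the adjusted difference, its 95% CI and the two-sided P value will be reported. The same model will be used for global longitudinal strain and coronary flow reserve. Within-arm changes will be descriptive.*

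An unpaired t test would also cure the defect. ANCOVA is preferred because its power is higher than that of either unpaired test at every correlation examined.

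The cost is one or two sentences. Baseline and follow-up stress echo are already planned in all patients. With ANCOVA no change in sample size is needed: power is about 81% even at 24 per arm and r = 0.3. That assurance does not extend to the unpaired tests. At 25 per arm the test on follow-up values has 79% power, and the test on change has 65% at r = 0.3.
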